4.8.1 Adverse events

An adverse event (AE) is defined as any untoward medical occurrence in a patient or clinical investigation subject administered a pharmaceutical product that does not necessarily have a causal relationship with the product. An

AE can therefore be any unfavorable and unintended sign (including a new, clinically important abnormal laboratory finding), symptom, or disease, temporally associated with the product, whether related to the product.

AEs are collected from the time of the informed consent is signed until the follow-up call is completed. For each AE, the following data will be recorded in the eCRF: verbatim text, start date, stop date, outcome, investigator's assessment of severity, assessment of seriousness, relationship to IP, action taken with IP, and discontinuation due to AE. The verbatim text will be coded by using Medical Dictionary for Regulatory Affairs (MedDRA) version 19.

- Outcome will be recorded as "FATAL"; "NOT RECOVERED/NOT RESOLVED"; "RECOVERED/RESOLVED"; "RECOVERED/RESOLVED WITH SEQUELAE"; "RECOVERING/RESOLVING"; or "UNKNOWN".
- Investigator's assessment of severity will be recorded as "MILD"; "MODERATE"; or "SEVERE".
- Assessment of seriousness will be recorded as "N" or "Y".
- Relationship to IP will be recorded as "NOT RELATED"; "POSSIBLY RELATED"; or "PROBABLY RE-LATED".
- Action taken with IP will be recorded as "DOSE NOT CHANGED"; "DRUG WITHDRAWN"; "NOT APPLI-CABLE"; "UNKNOWN"; "DOSE INCREASED"; "DOSE REDUCED"; or "DRUG INTERRUPTED".
- Discontinuation due to AE will be recorded as "N" or "Y".

A flag for related AEs will be calculated as:

- IF the relationship to IP is "POSSIBLY RELATED" or "PROBABLY RELATED", THEN set the related AE flag equal to "Y".
- OTHERWISE, set the related AE flag equal to "N".

A flag for AEs leading to study drug withdrawal will be calculated as:

- IF the action taken with IP is "DRUG WITHDRAWN", THEN set the AE leading to study drug withdrawal flag equal to "Y".
- OTHERWISE, set the AE leading to study drug withdrawal flag equal to "N".

Treatment emergent AEs (TEAEs) are defined as those AEs occurring or worsening after the first dose of IP and within 3 days of the last dose of IP. If an AE start date is completely missing (i.e., in which the day, month, and year are all unknown), then the AE start date will be set to the date of first dose of IP. For a partial AE start date, the following conventions will be used for imputing the AE start date:

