- When the year is present and the month and day are missing:
 - If the year of AE start = the year of first dose of IP, then the month and day will be set to the month and day of first dose of IP.
 - If the year of AE start < the year of first dose of IP, then the month and day will be set to December 31st.
 - If the year of AE start > the year of first dose of IP, then month and day will be set to January 1st.
- When the year and day are present and the month is missing:
 - If the year of AE start = the year of first dose of IP, then the month will be set to the month of first dose of IP.
 - If the year of AE start < the year of first dose of IP, then the month will be set to December.
 - If the year of AE start > the year of first dose of IP, then the month will be set to January.
- When the month and year are present and the day is missing:
 - If the year of AE start = the year of first dose of IP and

- \circ the month of AE start = the month of first dose of IP, then the day will be set to the day of first dose of IP.
- \circ the month of AE start < the month of first dose of IP, then the day will be set to the last day of the month.
- $\circ\,$ the month of AE start > the month of first dose of IP, then the day will be set to the 1st day of the month.
- If the year of AE start < the year of first dose of IP, then the day will be set to the last day of the month.
- If the year of AE start > the year of first dose of IP, then the day will be set to the 1st day of the month.
- If the imputed AE start date is after the AE stop date, then the AE start date will be set to the AE stop date.

For each AE, a treatment emergent flag will be calculated using the recorded AE start date (or imputed start date, where applicable).

• IF the date of first dose of IP \leq AE start date \leq date of last dose of IP + 72 hours, THEN set the treatment emergent flag equal to "Y".

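### SAP 4.8.1: when only the month of an AE start is missing, the imputed date can fall before first dose and the event loses its treatment-emergent flag, although less complete dates keep it

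*SAP*

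**What the plan says.** SAP 4.8.1 defines TEAEs as "those AEs occurring or worsening after the first dose of IP and within 3 days of the last dose of IP". The flag is computed from the recorded start date or, for a partial date, the imputed one. The start must be no earlier than the first dose and no later than the "date of last dose of IP + 72 hours, THEN set the treatment emergent flag equal to" Y.

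The same-year imputation rules are:

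- **Date completely missing:** "then the AE start date will be set to the date of first dose of IP".
- **Month and day missing, year of first dose:** "then the month and day will be set to the month and day of first dose of IP".
- **Day missing, month and year of first dose:** the day becomes the first-dose day.
- **"When the year and day are present and the month is missing", year of first dose:** "then the month will be set to the month of first dose of IP". The recorded day stays.

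One adjustment follows: "If the imputed AE start date is after the AE stop date, then the AE start date will be set to the AE stop date". It can only move a start date earlier. Nothing in the section moves an imputed date forward to the first dose.

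**The concern.** The first three rules place an uncertain start on the first-dose date, so the event is flagged. The missing-month rule does so only by chance. If the recorded day is earlier in the month than the first-dose day, the imputed start precedes treatment and the flag cannot be Y. A record giving only the year is therefore counted, while one that also gives the day of the month can drop out. The stop date is not used to rescue it.

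Treatment lasts 6 weeks (Protocol 10.2), so dosing crosses a month boundary for almost every subject and the situation can arise for nearly any first-dose date after the 1st. The flag feeds the TEAE lines of the overall AE summary (SAP 5.5.2) and the TEAE tables by SOC and preferred term, drug withdrawal, relationship and severity (SAP 5.5.2.1 and 5.5.2.3 to 5.5.2.5).

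**Working it through.** The plan states no figure to reproduce, so the check applies its rule to dates.

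**Inputs.** Treatment is 42 days (Protocol 10.2, 6 weeks). The flag runs to 3 days after last dose (SAP 4.8.1), so the window is 42 + 3 = 45 days. Screening is up to 28 days (Protocol 10.2), and AEs are collected from consent (SAP 4.8.1). Assumptions: onset equally likely on each day, onset in the calendar year of first dose, dates taken from 2018.

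**Rule.** Imputed start = (recorded day, first-dose month, year). The flag is lost when recorded day < first-dose day.

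**One case.** First dose 20 July; AE start recorded as day 5, month unknown, 2018; stop date 25 August.

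- Imputed start: 5 July. It is not after the stop date, so the stop-date adjustment does nothing.
- 5 July < 20 July, so the flag is not Y, although 5 August is a possible start and lies on treatment.
- Had the day been missing as well, the start would be 20 July and the flag Y.

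**All onsets for that first dose.** The window is 20 July to 2 September. Days that lose the flag are 1-19 August (19) and 1-2 September (2): 21 of 45 = 47%.

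**All first-dose dates.**

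- Every 2018 first-dose date with same-year onsets: 5,916 of 15,435 = 38.3%.
- Only first-dose dates whose 45-day window ends within the year: 38.9%.
- By first-dose day: 0 of 45 for the 1st, rising to 43 of 45 for 31 July and 44 of 45 for 31 January.
- A further 101 of 15,435 (0.7%) give a date that does not exist, such as the 31st of a 30-day month.

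**The opposite error.** The same rule applied to onsets in the 28 days before first dose, for first doses from 1 February to 16 November:

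- 3,801 of 8,092 = 47% are imputed into the treatment window. Example: first dose 20 July, true onset 25 June, imputed 25 July.
- Over the same first-dose dates, on-treatment losses are 5,003 of 13,005 = 38%.
- At equal daily onset rates the net shortfall is (5,003 − 3,801) / 13,005 = 1,202 / 13,005 = 9% of on-treatment onsets with this pattern.

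The 47% is taken before the stop-date adjustment. A screening event with a recorded stop before first dose is pulled back to that stop date and is correctly left unflagged. The over-count therefore concerns events continuing past first dose or lacking a stop date, and where stop dates are recorded the net shortfall lies between 9% and 38%.

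**With the change below.** A true on-treatment onset has a stop date that is missing or on/after first dose, so every one of the 5,916 losses is recovered. The 101 impossible dates still need a convention.

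**The case against.** **The rule errs in both directions.** A reader might infer that safety counts are biased downward by about 39%. The documents do not support that. The 38-39% is a share of on-treatment events that already have this date pattern, and it is partly offset by screening events imputed into treatment. In the worked case 5 July falls within the screening period and could be the true date. The net effect depends on AE rates before and after first dose, which the documents do not give. This stands.

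**The pattern should be rare.** It needs a known day and year with an unknown month. AEs are reviewed at weekly visits, monitors compare eCRF entries with source (Protocol 15.3.1), and data go through queries and consistency checks (Protocol 15.3.2). The documents give no frequency. This also stands, and it limits the weight of the point.

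**Little depends on the flag.** A reader might infer that a lost event is conspicuous in a trial of 42 to 64 subjects. One subject is indeed 1/21 = 4.8 to 1/32 = 3.1 percentage points of an arm. But no event disappears: all AEs are listed, SAE and death summaries are not restricted to TEAEs (SAP 5.5.2 and 5.5.2.2), no safety hypothesis is tested (SAP 5.5), and the rule does not depend on treatment arm.

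**A general floor at first dose would be wrong.** An AE recorded as June with the day unknown, against a 20 July first dose, certainly began before treatment, and SAP 4.8.1 rightly imputes 30 June. Protocol 11.1.2 has worsening of a pre-treatment event recorded as a new AE, so moving the June event forward would create a false TEAE. This stands and confines the fix.

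None of these points explains why a record with more information should be flagged less readily than one with less.

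**Conclusion.** The missing-month, same-year rule gives a wrong flag as written and departs from its sibling rules. Under uniform onset over 45 days, about 38-39% of on-treatment onsets with this date pattern lose the flag, ranging from none for a first dose on the 1st to nearly all for the 31st. About 47% of onsets in the 28 days before first dose go the other way before any stop-date adjustment. These are shares of a probably rare kind of record, not effects on the trial's TEAE counts.

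The convention of resolving doubt towards treatment-emergent is inferred from the sibling rules; the SAP does not state it. SAP 4.5 reasons in the same way for medications with a wholly unknown date, treating them as concomitant unless the end date precedes study drug. The SAP also gives no explicit N branch, so strictly the event is not Y rather than N; the TEAE tables come out the same. This is worth correcting, but it is not a threat to the safety conclusions.

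**What to change.** In SAP 4.8.1, within the rule for a missing month in the first-dose year only, add: if the imputed start date is before the first dose and the AE stop date is missing or on/after the first dose, set the start date to the date of first dose. Leave unchanged the rules for start dates known to lie in an earlier month or year.

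The cost is one sentence and one line of code before database lock. The downside is that some true screening AEs that are ongoing at first dose, or have no stop date, would be flagged as TEAEs. The sibling rules already accept that trade-off. The change does not remove the existing imputation of some screening onsets into treatment. If the sponsor intends the present asymmetry, the SAP should say so and give the reason.

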### 11. ADVERSE EVENTS

### 11.1 Definition of Adverse Events, Period of Observation, Recording of Adverse Events

### 11.1.1 Adverse Event Collection

An AE is defined as any untoward medical occurrence in a patient or clinical investigation subject administered a pharmaceutical product that does not necessarily have a causal relationship with the product. An AE can therefore be any unfavorable and unintended sign (including a new, clinically important abnormal laboratory finding), symptom, or disease, temporally associated with the product, whether related to the product. An AE will be considered treatment emergent if it occurs after the first dose of IP and within 3 days of a subjects last dose of IP.

All AEs are collected from the time of the informed consent is signed until the follow-up call is completed as stated in Section 10.1.7. This includes events occurring during the screening phase of the study, regardless of whether investigational product is administered. Where possible, a diagnosis rather than a list of symptoms should be recorded. If a diagnosis has not been made, then each symptom should be listed individually. All AEs should be captured on the appropriate

AE pages in the eCRF and in source documents. In addition, to untoward AEs, unexpected benefits outside the investigational product indication should also be captured in the source documents and AE eCRF.

All AEs must be followed to closure (the subject's health has returned to his/her baseline status or all variable have returned to normal), regardless of whether the subject is still participating in the study. Closure indicates that an outcome is reached, stabilization achieved (the investigator does not expect any further improvement or worsening of the event), or the event is otherwise explained. When appropriate, medical tests and examinations are performed so that resolution of an event(s) can be documented.

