### 11.1.2 Severity of Adverse Events

The severity of AEs must be recorded during the course of the event including the start and stop dates for each change in severity. An event that changes in severity should be captured as a new event. Worsening of a pre-treatment events, after initiation of investigational product must be recorded as new AEs. For example, if the subject experiences mild, intermittent headaches prior to dosing with IP however the headache intensity increases to moderate after the first dose of IP, a new AE of moderate intermittent headaches is to be recorded in the source documents and eCRF.

The medical assessment of clinical severity of an AE will be determined using the following definitions:

Mild Usually transient and may require only minimal treatment or therapeutic intervention. The event does not generally interfere with usual activities of daily living.

Moderate Usually alleviated with additional specific therapeutic intervention. The event interferes with usual activities of daily living, causing discomfort but poses no significant or permanent risk of harm to the subject.

Severe Interrupts usual activities of daily living, or significantly affects clinical status, or may require intensive therapeutic intervention.

It is important to distinguish between severe AEs and SAEs. Severity is a classification of intensity whereas an SAE is an AE that meets serious criteria, as described in Section 11.1.4.3.

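### The SAP's treatment-emergent flag tests only the AE start date, so a pre-treatment event that eases after first dose is flagged as a TEAE against the SAP's own definition

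*SAP*

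**What the plan says.** Four rules bear on this point.

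- **Definition.** SAP 4.8.1 defines TEAEs as "those AEs occurring or worsening after the first dose of IP and within 3 days of the last dose of IP". Protocol 11.1.1 is shorter and does not mention worsening: "An AE will be considered treatment emergent if it occurs after the first dose of IP and within 3 days of a subjects last dose".
- **Derivation.** SAP 4.8.1 then says "a treatment emergent flag will be calculated using the recorded AE start date (or imputed start date, where applicable". The condition is that the start date lies from the date of first dose to the date of last dose plus 72 hours. It contains no severity term and does not look back to earlier records.
- **Recording of severity.** Protocol 11.1.2 requires severity to be recorded "including the start and stop dates for each change in severity" and adds "An event that changes in severity should be captured as a new event". A further sentence says that a pre-treatment event that worsens after dosing starts is recorded as a new AE, and the example given is a headache going from mild to moderate.
- **Collection period.** AEs are collected from consent. Protocol 11.1.1 is explicit about the time before dosing: "This includes events occurring during the screening phase of the study, regardless of whether investigational product is administered".

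**The concern.** The definition asks whether the event began or became worse on treatment. The flag asks only whether a record began on treatment. These agree as long as a post-dose record means a new or worsened event. Protocol 11.1.2 breaks that link, because its general sentence opens a new record for any change in severity, including a change for the better.

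The situation can arise in this trial. Subjects on ADHD medication stop it 5 days (stimulants) or 14 days (nonstimulants, or clonidine at night) before Baseline, and AEs are recorded at the washout call and at the Baseline Visit (Protocol 9.9.4, 10.1.2, 10.1.3). A symptom that appears in that period can still be present at first dose and ease later.

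The TEAE tables in SAP 5.5.2 (any TEAE, related TEAEs, TEAEs by system organ class and preferred term, by maximum relationship and by maximum severity) all depend on treatment-emergent status. A wrong flag therefore carries through to the main safety summaries, and no later step removes it.

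**Working it through.** The plan gives no figure to reproduce here. The check applies the flag literally to records created under Protocol 11.1.2 and compares the result with the SAP definition.

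**Illustrative days (assumption).** First dose Day 1 and last dose Day 42, so the flag window is Day 1 to Day 45 (42 + 3). Pre-dose events start on Day -7 and change severity on Day 5.

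| Case | Start date of the record tested | SAP flag | Occurred or worsened after first dose? |
|---|---|---|---|
| New AE, no pre-dose record | Day 10 | Y | Yes |
| Pre-dose mild, becomes moderate | Day 5 | Y | Yes |
| Pre-dose moderate, becomes mild | Day 5 | Y | No |
| Pre-dose severe, becomes moderate | Day 5 | Y | No |
| Pre-dose severe, becomes mild | Day 5 | Y | No |
| Pre-dose moderate, unchanged | Day -7 | not flagged | No |

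Flag and definition agree in three cases and disagree in the three where the event improves. Worsening is handled correctly because the worsened event gets its own post-dose start date.

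**Size of one misflag.** Part A plans 42 randomized subjects, possibly raised to 64, at 1:1.

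- 42 / 2 = 21 per arm, and 1 / 21 = 4.8 percentage points.
- 64 / 2 = 32 per arm, and 1 / 32 = 3.1 percentage points.

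These figures assume that every randomized subject is in the safety set. SAP 5.5.2.1 counts a subject once per system organ class and preferred term, so the increment arises only if the subject has no other TEAE in that row. The documents report neither how many subjects have a pre-dose AE nor how many of those ease after dosing, so the number of misflagged subjects cannot be calculated.

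**What a repaired rule must handle.** Two harder sequences test any severity condition.

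- *Easing in steps:* severe before dosing, moderate on Day 4, mild on Day 10. The Day 10 record follows one that began after first dose. A rule that looks back only one record, to one that began before dosing, would still flag it. The whole sequence has to be linked.
- *Easing before dosing, then worsening:* severe in early screening, mild at first dose, moderate on Day 5. This is a true worsening on treatment. Comparison with the worst pre-dose severity would suppress it (moderate does not exceed severe). Comparison with the severity ongoing at first dose keeps it (moderate exceeds mild). The second comparator also matches SAP 4.8, where the safety baseline is the last assessment before first dose.

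**The case against.** **The worsening sentence may be the governing rule.** The strongest reply is that Protocol 11.1.2 has a specific instruction for pre-treatment events, that it covers worsening only, and that its single example is a worsening. If it were the only rule for such events, an easing event would keep its original record and pre-dose start date, and the start-date flag would implement the definition. Sites could well record this way. But the general sentence comes first, is not restricted to on-treatment events and gives no direction, and the worsening sentence adds to it without limiting it. As written, the step-down record is required.

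**The protocol's definition is simpler.** A split record might be said to occur after first dose in the sense of Protocol 11.1.1. The contradiction is therefore clearest within SAP 4.8.1, between its definition and its own flag.

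**The practical effect is limited.** This stands. Safety is descriptive with no hypothesis tests (SAP 5.5), and all AEs are listed by subject. A step-down record enters the maximum-severity table at its lower grade, and it reaches the related-TEAE count only if the investigator judges it related. The error adds events and hides none.

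**Stronger readings to avoid.** A reader might infer that the error counts against AEVI-001, on the reasoning that an effective drug would ease more pre-dose symptoms. The documents do not support this: the rule is identical in both arms and nothing shows that easing differs between them. A reader might also infer a substantial inflation of TEAE rates, but no rate is given from which to derive one. Nor does the start-date rule miss worsening.

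**Conclusion.** The flag in SAP 4.8.1 is wrong as written. Combined with the recording rule in Protocol 11.1.2, it classifies a pre-treatment event that eases after first dose as a TEAE, which the SAP's definition excludes. The conclusion rests on reading the general severity-change sentence as it stands, without a direction. It affects only events that are moderate or severe at first dose and step down within the flag window. The per-subject increments above are upper limits for a single row at the planned arm sizes, and the total effect is unknown. The correction is worth making because a stated derivation contradicts its own definition in the main safety tables and the data needed to repair it are already collected.

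**What to change.** In SAP 4.8.1, before the flag is set:

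1. Within each subject, link records of the same preferred term into one chain where the stop date of one falls on the day of, or the day before, the start date of the next.
2. If the chain began before first dose, flag a post-dose record in the window as treatment emergent only if its severity is greater than the severity ongoing at first dose (the last pre-dose severity).
3. Set every other record in that chain to not treatment emergent, including later steps of an easing in several steps.
4. Leave records not linked to a pre-dose event under the existing start-date rule.

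This clears the three improvement cases and both steps of the stepwise easing. It keeps new events, the mild-to-moderate worsening, and the subject who eased before dosing and then worsened.

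The cost is one derivation rule and its programming. Severity, start and stop dates and the coded term are already captured. The SAP is to be finalized before database lock and unblinding, so the change belongs before then. The downside is that SAP 4.8.1 lists no eCRF field linking records of one event, so matching on contiguous dates may occasionally merge separate episodes. Linked chains should therefore be reviewed before unblinding.
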